5.3.2 Determination of the Start of the Clinical Qualifying Event

For the purposes of the primary outcome analyses, the relapse start day will be used. The time of the event occurs at the start of the qualifying clinical event period (e.g., first of the 7 consecutive use days or start of the 4 consecutive weeks of use). If both of the criteria above (a and b) are met, then the earlier of the two relapse start dates will define the day that the relapse criterion met for the purposes of primary outcome analyses.

When a participant’s data indicates four consecutive weeks of use, the reason the first week was defined as a use week will be used to determine the start of the qualifying clinical event period. The first use week could be due to either a self-report of at least one day of use, a urine sample positive for non-protocol opioids, failure to provide a urine sample or some combination of these reasons. The following table outlines how the start of the clinical qualifying event will be determined in the case of a participant having four consecutive weeks of use.

Table 4: Determination of the Start of the Clinical Qualifying Event			
Reason for First Use Week			Start of the Clinical Event
Missing UDS	Positive UDS	Self-report of at least one day	
*		*	Date of first self-reported use
	*	*	Day of first self-reported use
		*	Day of first self-reported use
	*		Day of positive urine drug screen
*			First study day of the first use week period as defined by the protocol calendar

5.3.3 Primary Outcome Analysis Methods

Since the results of the interim analysis indicated a differential treatment initiation rate assessment, the data analysis modification will be employed. As noted in Section 3.2, if there is a differential treatment initiation rate in the early randomizers group, an interaction term for the treatment by randomization timing variables will be incorporated into the final analysis model.

Data will be analyzed using a Cox proportional hazards model. The model is as follows:

$$\log h(t | CUF) = \log h_0(t | CUF) + \beta_1 * Treatment + \beta_2 * TIMING + \beta_3 * CTP + \beta_4 * STRATA + \beta_5 * Treatment * TIMING$$

where h is the hazard rate, roughly defined as the probability per time unit that a case that has not relapsed to the beginning of the respective interval will relapse in that interval. Conceptually, it can be thought of as the number of relapse per time units in the respective interval, divided by the average number of non-relapse cases at the mid-point of the interval. The quantity h0 is an arbitrary baseline hazard rate.

The SAS PHREG procedure will perform survival analysis based on the Cox model to estimate the hazard ratio for the treatments. The 95% Wald Confidence limits will be estimated.

The following SAS Code will be used to analyze the data:

```
PROC PHREG;
    CLASS TREATMENT (REF='BUP-NX') TIMING (REF='Late');
    MODEL TIME*STATUS = TREATMENT TIMING CTP STRATA
    TREATMENT*TIMING;
    HAZARDRATIO TREATMENT;
RUN;
```

The variables included in the SAS code are described as follows:

- TREATMENT- This variable defines the randomized treatment assignment. (BUP-NX or XR-NTX)
- TIME- Time to relapse
- STATUS- Censoring variable
- CTP- CTP
- STRATA- Randomization Stratification factor pertaining to the baseline opioid severity level classified as <6 bags (Low Severity) or ≥ 6 bags (High Severity).
- TIMING- Binary baseline variable (early vs. later randomization as noted in Section 5.1 defined as either 'Late' or 'Early').

The initial analysis will be the construction of the asymptotic 95% CI for the hazard ratio of the difference between the treatment arms in the time to event distribution for the primary outcome. The study arm success rates with confidence intervals at week 24 and the difference in success rate at that time point and associated confidence intervals will be constructed.

If the data analysis modification is implemented, the binary baseline variable (early vs. later randomization as previously defined) is included in the primary outcome analysis (outcome = time-to-relapse) as a covariate, a priori. The early vs. late randomization covariate by treatment interaction is included in the primary outcome analysis. If the covariate (early vs. late randomization) by treatment interaction is significant at $P < .10$, then the interaction term is retained in the final model. To characterize the interaction, the effect of treatment assignment (which includes the interaction and the main effect for treatment) (i.e., the difference in time-to-relapse between treatments) is estimated separately in early vs. late randomizers, and these two separate estimates become the primary findings of the study. If the covariate (early vs. late randomization) by treatment interaction is not significant ($p \geq .10$) then the interaction term will be removed from the model and the main effect estimate will be the primary finding of the study. Exploratory analyses will also evaluate whether the primary outcome measure of time-to-relapse is associated with the number of hours between last licit or illicit opioid use and randomization, that is, a continuous measure of the randomization timing. Both linear and non-linear effects will be explored as potential effect modifiers.

The Cox proportional hazard model is based on the following assumptions. First, there is a proportional hazards assumption, such that if an individual has a risk to opioid use at initial time point that is twice as high as that of another individual, then at all later times the risk of opioid use remains twice as high. Secondly, factors such as the way participants are recruited into a study and the determination of relapse remains constant over the period of the study i.e. censoring should be independent of an event (relapse) happening. The proportional hazards assumption will be assessed by testing of the time to relapse variable and the corresponding covariates of interest. If the proportional hazards assumption is not met, the final model will incorporate a time-dependent variable for the non-proportional predictors in the Cox model.

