1.5 Randomization

Immediately following the final assessment of eligibility, participants will be randomly assigned to one of the two conditions: XR-NTX or BUP-NX. Random assignment will be on a 1:1 ratio to one of the two conditions. A restricted randomization plan will be used with centralized, automated, randomized block assignments. Randomization will be stratified by two factors, site and pre-detoxification level of opioid use. While there will be important and otherwise uncharacterized differences between sites – including state and local treatment service environments, opioid misuse epidemiology, and patient-level customs regarding treatment, medications, and clinical trial participation – the level of heroin and other opioid use will likely be an important independent predictor of treatment retention and rates of negative urines as has been demonstrated in recent analysis of naltrexone opioid trials (Sullivan et al 2006; Carpenter et al 2009; Brooks et al 2010). The level of opioid use at treatment entry is a binary classification, operationally defined as 6 or more bags (or equivalent) IV heroin per day (≥ 6 bags/day) over the 7 days prior to entry into the treatment program versus less than 6 bags (or equivalent) IV heroin per day (< 6 bags/day) or other routes of administration or other opioids.

Eligible participants will be randomized in a 1:1 ratio to the BUP-NX and XR-NTX arms. The randomization process will be performed by computer at a centralized location. Randomization will be stratified by site and pre-detoxification level of opioid use [≥ 6 or more bags (or equivalent) IV heroin per day (≥ 6 bags/day) over the 7 days prior to entry into the treatment program versus less than 6 bags (or equivalent) IV heroin per day (< 6 bags/day) or other routes of administration or other opioids]. The block size chosen will be adequate to ensure approximate treatment balance. The number in each treatment group will never differ by more than a factor of $KB/2$ where B is the block size and K is the number of strata.

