Beyond a sample size of 150 to 200 patients per group, further increments in sample size (200 per group, 250 per group, 300 per group, etc.) yield diminishing returns in terms of only relatively small further narrowing of the 95% confidence interval. The rationale for increasing the total sample size to N ~600, in the event of a significant difference in induction success rate among early randomizers, is that given the current ratio of early to late randomizers, N ~600 total will yield approximately 250 early randomizers and 350 later randomizers. 350 late randomizers (N = 175 per treatment group) is close to the 400 (N = 200 per group) originally planned, and will yield a very similar (only slightly wider) 95% confidence interval. This will preserve the intent to achieve a relatively precise estimate of the difference in relapse rates among late randomizers.

Figure 1: Simulation results for the 50th and Upper 95th percentile of the 95% Confidence Interval Widths for the Hazard Ratio, selected sample sizes with lambda=0 and lambda=0.678

The decision theoretic properties of n=200/arm is evaluated further under a decision theoretic approach and using the logrank test. With two-sided alpha = 0.05, N = 400 total participants provides 90% power to detect a hazard ratio of .63 for the second treatment. Table 2 provides additional characterization of power characteristics of the sample size.

Table 2: Detectable Alternatives and Power for 2-tailed 5% level logrank test without censoring Null distribution has a 40% 6 month success rate, N1=N2=200		
Power (%)	Hazard Ratio	6 Month Survival Rate (%) under the Alternative
90.0	.633	56.0
80.0	.678	53.8

Note that inclusion of the baseline level of opioid dependence severity stratification variable in the statistical model as a covariate may increase power and narrow the confidence limits on treatment hazard ratios, should divergent success rates be present in the strata groupings.

Secondary analyses of moderators of treatment effect are important to trial sample size selection. With approximately 200 XR-NTX cases evenly split between two levels of a classifying variable, we would have 79% power to detect, using a two-tailed 5% level test of a binary endpoint, a 20 percentage point difference between the groups. Thus the selected sample size would be relatively robust in its ability to determine whether there are important differences in therapeutic success rates for major demographic or baseline clinical factors.

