5.4 Secondary Analyses of Primary Outcome Measure

Subsequent analyses will explore the treatment effect as a function of time, stratification variables and other factors that may have differential impact on treatment success. The analyses will first model the time to event primary outcome measure as a function of treatment assignment (XR-NTX vs. BUP-NX), opioid dependence severity stratum, site, and the two way treatment interaction terms (site by treatment and stratum by treatment) in a proportional hazards regression model. The Cox model previously described in the primary outcome analysis can separately incorporate covariates that are fixed (at baseline). The constancy of the relative hazard assumption will be examined via the interaction of treatment and time, and the interaction between treatment and baseline severity will be tested.

If treatment by site interaction is significant, we will further investigate if the interaction is quantitative or qualitative. A quantitative interaction between treatment and site will indicate that the treatment differences are in the same direction across sites but the magnitude differs from site to site, while a qualitative interaction reveals that substantial treatment differences occur in different directions in different sites. As indicated by Gail and Simon (1985), the existence of a quantitative interaction between treatment and site does not invalidate the analysis in pooling data across centers. Hence we will analyze the data ignoring the treatment-by-site interaction. But when there is a qualitative interaction the treatment effect itself would not make any sense and any kind of analysis claiming a common treatment effect will be questionable.

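### The primary Cox code in SAP 5.3.3 gives the eight-level site factor a single coefficient, so the model does not adjust for site

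*SAP*

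**What the plan says.** SAP 5.3.3 introduces a PROC PHREG block with "The following SAS Code will be used to analyze the data". The class statement is "CLASS TREATMENT (REF='BUP-NX') TIMING (REF='Late" (shown up to the TIMING reference level), and nothing else is declared categorical. The model statement is "MODEL TIME*STATUS = TREATMENT TIMING CTP STRATA", followed by the treatment-by-timing interaction. The equation above the code has one term for site, β₃·CTP, and the variable list explains CTP only by repeating its name.

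Site is not a numeric quantity in this trial. Protocol 7.3 gives 8 sites, and the SAP table shells list eight by name. SAP 1.5 states "Randomization will be stratified by two factors, site and pre-detoxification level of opioid use" and gives the reason for including site: "While there will be important and otherwise uncharacterized differences between sites". SAP 5.4 plans "the two way treatment interaction terms (site by treatment and stratum by treatment", and so treats sites as separate categories.

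The 5.3.3 model also carries the P<.10 test of the treatment-by-timing interaction. If that test is met, the early and late treatment effects are estimated separately and "these two separate estimates become the primary findings of the study".

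**The concern.** In PROC PHREG a variable that appears in MODEL but not in CLASS is read as a numeric covariate. A single coefficient for eight unordered sites then has two possible meanings, and neither adjusts for site. If CTP is held as text, the printed step cannot run and has to be repaired after the SAP is final. If CTP is held as a number, the step runs without complaint, forces the log hazard to change by equal steps along whatever order the sites were numbered, and gives results that change when the sites are renumbered.

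The primary hazard ratio and its 95% confidence interval come from this model, and so does the decision to report one hazard ratio or two. The timing terms are the more exposed part, because randomization is stratified by site and opioid use level but not by timing, so the mix of early and late randomizers can differ between sites.

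**Working it through.** **1. The plan's own figures.** SAP 3.3 gives 90.0% power at HR .633 and 80.0% at HR .678, for 200 per arm, 40% six-month success in the reference arm, two-sided 5%. With events d = 400 × [(1 − .40) + (1 − .40^HR)]/2 and power = Φ(|ln HR|·√d/2 − 1.96):

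- HR .633: .40^.633 = .560, d = 208.0, .4573 × 7.211 − 1.96 = 1.338, power .910.
- HR .678: .40^.678 = .537, d = 212.5, .3886 × 7.289 − 1.96 = .873, power .809.

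Both agree with the plan. They are unadjusted logrank figures, so site coding does not alter them.

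**2. Counting coefficients.** Treatment, timing, severity stratum and the interaction take one each, 4 in all. As printed, site adds 1, for a total of 5. A factor with 8 levels needs 8 − 1 = 7, for a total of 11. Six site contrasts are therefore forced to zero. The severity stratum is also outside CLASS, but it is binary, so nothing is lost if it is coded numerically.

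**3. Size of the effect if site is numeric.** The full 5.3.3 model was simulated with site as seven indicators and as one line, using Efron ties in both so that site coding is the only difference.

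- From the plan: "N ~600 total will yield approximately 250 early randomizers and 350 later randomizers" (SAP 3.3); 8 sites; control hazard −ln(.40)/168 = .005454 per day; HR .633; no relapse before Day 21; follow-up to Day 167.
- Assumed, because the documents give no values: 75 per site (600/8); 1:1 allocation within site and severity; severity split 50/50 with no effect; early share from 10% to 78% across sites; between-site SD of the log hazard of 0, .15, .3 or .5. An SD of .3 puts a site one SD above average at a hazard ratio of exp(.3) = 1.35; for .5 it is exp(.5) = 1.65.
- 500 trials per setting, 12 random site numberings per trial. Monte Carlo SE is about 1 point for rates near .05 and 1.5 points for power near .88.

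| Assumed site SD | 0 | .15 | .3 | .5 |
|---|---|---|---|---|
| Late HR, seven indicators | .625 | .622 | .629 | .627 |
| Late HR, one line | .627 | .626 | .638 | .648 |
| Ratio of late log HRs, line/indicators | .993 | .986 | .970 | .930 |
| Overall HR without interaction, indicators | .625 | .625 | .632 | .627 |
| Overall HR without interaction, line | .627 | .629 | .641 | .648 |
| Power for late effect, indicators | .886 | .876 | .882 | .878 |
| Power for late effect, line | .888 | .877 | .867 | .827 |
| Highest/lowest late HR over 12 numberings (median) | 1.013 | 1.018 | 1.029 | 1.047 |
| P<.10 decision differs somewhere among 12 numberings, HR .633 in both groups | 2% | 3% | 4% | 8% |
| Same, late HR .633 and early HR 1.0 | 4% | 6% | 8% | 14% |

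The line's late log HR differs from the indicators' by at most 0.22 SE on average. Power for the overall effect is .97 to .99 either way. Under the null, the late effect is rejected in .054 to .064 of trials with indicators and .048 to .062 with the line.

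**4. A second simulation.** With 300 runs per setting and site SDs of 0, .2, .4 and .6, the late HR for line against factor was .631/.629, .637/.633, .641/.627 and .660/.632. A 6-df likelihood ratio test rejected the straight line in 5–6%, 58–65%, 93–96% and 99–100% of runs. At SD .6 the sampling SD of the timing coefficient was about .25 with the line and .17 to .18 with the factor.

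**The case against.** The harmful branch is not shown to apply. The same CLASS line uses text levels and the shells name the sites, which leans toward text storage; then the step fails visibly and no wrong estimate is produced. The block also lacks a censoring value for STATUS, so it must be edited before use, and SAP 3.6 allows for some adjustment of analyses. SAP 5.4 treats site as categorical, which suggests a slip rather than an intention. Protocol 12.4 names site only in the subsequent analyses.

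On size, allocation is 1:1 within site, so site does not confound treatment. The pull toward 1 is what a Cox model shows when a prognostic factor is left out: in a re-run at SD .5 (250 trials) the late HR was .629 with indicators, .649 with the line and .652 with no site term. The any-of-12 rates also overstate the practical risk, because only one numbering would be used. In that re-run, two random numberings disagreed on P<.10 in 1.2%, 0.8%, 1.6% and 2.4% of trials at SD 0, .15, .3 and .5 (HR .633 in both groups). The line disagreed with the indicators in 2.4% to 5.6%, but so did a model without site, in 2.0% to 5.6%.

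Most of this stands as a limit on size. It does not rescue the code. A general allowance for adjustment does not say how site is handled, and nothing else in the SAP corrects the block. The comparison with no site term shows that the line performs almost as if site had been omitted, although the SAP's own model includes it.

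**Conclusion.** The concern holds, as a minor error in a stated primary-analysis rule. As printed, the model cannot adjust for eight sites: with text codes it does not run, and with numeric codes it fits a trend over arbitrary labels. The reading of the code is certain. The size applies only to the numeric case and to assumed site differences.

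Under those assumptions the late log hazard ratio shrinks by about 1% at SD 0 to .15, 3% at .3 and 7% at .5. The power cost is within 1.5 points up to SD .3 and about 5 points at .5 (.878 − .827 = .051). Type I error is not inflated. The choice between one primary hazard ratio and two depends on the numbering in a small share of trials, about 1% to 2.5% for any two numberings at HR .633 in both groups. The spread of early randomizers across sites is also an assumption. That site belongs in the primary model rests on the SAP's own equation, not on Protocol 12.4.

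**What to change.** Choose one of two forms and state it in SAP 5.3.3. Either add CTP to the CLASS statement with a named reference site and replace β₃·CTP in the equation with seven site indicators, or remove CTP from MODEL and stratify the baseline hazard by CTP, with the equation written to match. If the severity variable is held as text, put it in CLASS as well.

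The cost is one line of code and one term in the equation, with no effect on data collection or participants. With no site differences the indicators cost essentially no power (.886 against .888). The same edit can state which STATUS value means censored and name the tie method; these are missing details and not part of the error.

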12.2 Rationale for Sample Size and Statistical Power

Original Projected Sample Size: 200 per treatment group. N = 400 total.

Data Analysis Modification Projected Sample Size: ~300 per treatment group. (N~600 total sufficient to enroll 350 late randomizers).

[figure not shown]
Rationale: The primary outcome is the time to relapse as defined above. Meta-analyses of randomized controlled trials of BUP-NX maintenance treatment for opioid dependence suggest that approximately 50% of patients are retained in BUP-NX treatment with good clinical outcome over 6 months.² Extended release naltrexone preparations have had few prior randomized comparisons but observations from a recent Russia-based trial evaluating the XR-NTX dose and formulation proposed for this trial had good results with 53% receiving all monthly injections and retained for 6 months. Direct randomized comparison of these approaches has not been performed.

We evaluate the anticipated variability of the primary terminal results by simulating under exponential distributional assumptions with event grouping over the first 21 days and using proportional hazards without censoring. Let one treatment have a 6-month success rate of 40% with exponential failure. We use a lower success target than indicated in the above paragraph because the use of the early randomization time point is expected to increase the percentage of

participants who are failures. There would be minimal impact on detectable alternatives if a higher 50% success rate was used. From the plot below, we observe that the 95% CI width for the hazard ratio for the 50th percentile of the simulation results under both the null and alternative hypotheses decreases by 31%, 19%, and 14% as the sample size increase by 50/arm from a base of 50/arm. CI width decreases by 11% when the sample size increases from 200/arm to 250/arm. We have selected 200/arm as subsequent precision improvements with this criteria are close to 10% per 100 sampling units.

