3.5 Software

All analyses will be performed utilizing SAS® version 9.3. All statistical tests will be conducted at the 5% Type I error rate (two-sided). When multiple tests are conducted, the chance of finding a significant difference in one of the tests, when in fact no difference exists, is greater than the stated Type I error rate. The investigators are aware of the multiple testing issues and will interpret results with caution and use confidence intervals where possible.

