5.3.1 Primary Outcome Criteria

Relapse assessment starts Day 21 post-randomization with the day of randomization as Day 0 and ends at the Week 24 visit. As noted above, relapse is defined in two ways:

- a) Four consecutive opioid use weeks
 - i) There are three ways that a use week can be established:
 - (1) Participant self-reports at least one day of use during that week

The self-report of use is measured between the weekly visits and thus does not always include the review of exactly seven days. At the weekly visit, if the previous visit was missed, the participant's daily self-report opioid use is assessed from the start of the current visit window (i.e. the beginning of the window as specified by the protocol calendar, see table below) to the day before the current visit. Conversely, if the previous visit was attended, the participants daily self-report opioid use is assessed from the previous visit attended day to the day before that current visit. Note, only participants self-report collected on or after Day 21 is used in evaluating whether the week is a use week. Thus, if the Week 3 visit is attended on Day 21, there cannot be a use week based on self-reported opioid use.

Visit Number	Target Day	Beginning Window (Days)	End of Window (Days)
00R	00	00	00
01	06	3	12
02	13	10	16
03	20	17	23
04	27	24	30
05	34	31	37
06	41	38	44
07	48	45	51
08	55	52	58
09	62	59	65
10	69	66	72
11	76	73	79
12	83	80	86
13	90	87	93
14	97	94	100
15	104	101	107

Table 3: CTN-0051 Protocol Calendar			
Visit Number	Target Day	Beginning Window (Days)	End of Window (Days)
16	111	108	114
17	118	115	121
18	125	122	128
19	132	129	135
20	139	136	142
21	146	143	149
22	153	150	156
23	160	157	163
24	167	164	195

(2) Participant provides a urine sample positive for non-protocol opioids

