	N	Mean (STD)	Median (Min, Max)	N	Mean (STD)	Median (Min, Max)
Randomization Timing Status						
Early Randomizers						
Late Randomizers						
Opioid Severity Level						
Low Severity						
High Severity						
Randomization Timing Status by Opioid Severity Level						
Early Randomizers and Low Severity						
Early Randomizers and High Severity						
Late Randomizers and Low Severity						
Late Randomizers and High Severity						
Inducted onto Study Medication						

¹ Percent days of illicit opioid use is calculated based on TLFB (only illicit use is provided) starting on Day 21 up until the day of relapse and is calculated as the number of opioid use divided by the total number of days in that time frame. Note, if the subject relapses immediately on Day 21, the percent days of opioid use is 100%. Missing TLFB days are defined as opioid use days.

Table 20: Summary of Abstinent Days¹ for Groups of Interest						
	BUP-NX (N=)			XR-NTX (N=)		
	N	Mean (STD)	Median (Min, Max)	N	Mean (STD)	Median (Min, Max)
Randomization Timing Status						
Early Randomizers						
Late Randomizers						
Opioid Severity Level						
Low Severity						
High Severity						
Randomization Timing Status by Opioid Severity Level						
Early Randomizers and Low Severity						
Early Randomizers and High Severity						
Late Randomizers and Low Severity						
Late Randomizers and High Severity						
Inducted onto Study Medication						

¹ Abstinent days are calculated based on TLFB starting on Day 21 up until the day of relapse and will be calculated as the number of days where opioids were not used. Missing TLFB days are defined as non-abstinent days.

Table 21: Summary of Number of Visits ‘Present and Clean’¹ for Groups of Interest						
	BUP-NX (N=)			XR-NTX (N=)		
	N	Mean (STD)	Median (Min, Max)	N	Mean (STD)	Median (Min, Max)
Randomization Timing Status						
Early Randomizers						
Late Randomizers						
Opioid Severity Level						
Low Severity						
High Severity						
Randomization Timing Status by Opioid Severity Level						
Early Randomizers and Low Severity						
Early Randomizers and High Severity						
Late Randomizers and Low Severity						
Late Randomizers and High Severity						
Inducted onto Study Medication						

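### The primary PHREG code names no tie method, so it runs on the Breslow default with an endpoint that creates ties; naming Efron or exact ties is a cost-free improvement, worth about 1% of the hazard ratio under the plan's own assumptions

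*SAP*

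**What the plan says.** SAP 5.3.3 commits to PROC PHREG ("The SAS PHREG procedure will perform survival analysis based on the Cox model to estimate the hazard ratio for the treatments") and prints the code to be run. The model statement begins "MODEL TIME*STATUS = TREATMENT TIMING CTP STRATA", adds the treatment-by-timing interaction, and ends without options. SAP 3.5 fixes the software: "All analyses will be performed utilizing SAS® version 9.3". Neither document mentions ties.

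The endpoint rules determine how many participants share an event date:
- SAP 5.3.1: "Relapse assessment starts Day 21 post-randomization with the day of randomization as Day 0 and ends at the Week 24 visit".
- SAP 5.3.2, Table 4: if the first of four use weeks counts only because the urine is missing, the event date is the "First study day of the first use week period as defined by the protocol calendar". A self-reported first use week takes the first day of use. A week that counts only on a positive urine takes the day of that urine.
- SAP Appendix A, Table 19 footnote, provides for immediate relapse: "if the subject relapses immediately on Day 21, the percent days of opioid use is 100".
- Protocol 12.2 ran its precision simulation "with event grouping over the first 21 days".

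SAP 5.3.3 also reports that differential treatment initiation was found, so the model carries the interaction. If that interaction reaches P<.10, the separate early and late hazard ratios become the primary findings.

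**The concern.** With few ties, the Breslow, Efron and exact methods agree. With many events on one date, Breslow keeps every tied case in the risk set for every other tied case. The fitted hazard ratio then moves toward the ratio of risks at that date, which is nearer 1 than the ratio of hazards.

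Here the first assessable date collects everyone who is already using or lost by then. SAP 3.2 expects induction failure to lead to relapse, so that group may be larger in one arm, chiefly among early randomizers. The model concerned supplies the primary hazard ratio, possibly the two timing-specific hazard ratios, and the test that chooses between them. The primary goal is estimation, so a tie method left to a software default deserves a check.

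**Working it through.** **1. Reproduce the plan's power figures.** Inputs are from SAP 3.3: 200 per arm, 40% reference success at 6 months, two-sided 5%.

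Events d = 200 × 0.60 + 200 × (1 − 0.4^HR). Power = Φ(|ln HR| × √d / 2 − 1.96).
- HR .633: d = 120 + 88.0 = 208.0; power 90.9% (stated 90.0%).
- HR .678: d = 120 + 92.5 = 212.5; power 80.9% (stated 80.0%).

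The figures reproduce. They rest on the logrank test, so the Cox tie method does not touch them.

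**2. Share on Day 21 under the same exponential (168 days).** Share = 1 − 0.4^(HR × 21/168).
- Reference arm: 10.8%.
- HR .678: 7.5%.
- HR 1.475 (= 1/.678): 15.5%.

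**3. What Breslow does at one tied date.** With one event time and two arms, setting the Breslow score to zero gives exp(β) = (d₁/n₁)/(d₀/n₀), the risk ratio. From step 2 that is .1554/.1082 = 1.44 against a true 1.475, about 2.6% too near 1 at that date. The rest of follow-up dilutes this.

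**4. Simulated fits under the design assumptions.** 1,000 replicates, 200 per arm, proportional hazards; CTP and STRATA left out.

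| True HR | Ties | Breslow | Efron | Shift |
|---|---|---|---|---|
| .678 | Day 21 only | .682 | .680 | 0.4% |
| .678 | Day 21, then all weekly | .682 | .676 | 0.8% |
| 1.475 | Day 21 only | 1.467 | 1.476 | 0.6% |
| 1.475 | Day 21, then all weekly | 1.460 | 1.478 | 1.2% |

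Without ties the two methods are identical. With a true effect, Breslow was nearer 1 in 93% to 99.9% of trials. At a true HR of 1 there was no material shift. The standard error of the log HR is 0.12 to 0.14, roughly ten times the shift or more.

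**5. Adding an induction gap (assumed).** SAP 3.2 gives .25 as the difference its decision rule can detect in early randomizers, with BUP-NX initiation at .85 or above. Neither document gives a Day 21 share by arm. Assume N = 600 (125 early and 175 late per arm), Day 21 mass of 15% (BUP-NX) against 40% (XR-NTX) in early randomizers and 10% in both late groups, and equal hazards afterwards (600 replicates):
- Early HR: 1.60 Breslow, 1.69 Efron (5%).
- Late HR: 0.99 both.
- Pooled HR: 1.24 and 1.27 (2.5%).
- Interaction at P<.10: 67.5% and 74.8% of trials.

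A grouped-data proportional-hazards fit in 60 replicates gave 1.675 early and 1.261 pooled; Efron gave 1.672 and 1.260 on the same data. Two further runs of the .25 early gap, with all of it on Day 21, gave early HRs of 1.39 against 1.49 and 1.37 against 1.47 (about 7% each). The second gave 1.15 against 1.18 pooled (about 2%).

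**6. Range of the assumption.**
- Spread: with half or all of the assumed induction failures spread over Days 21–30, the early shift falls to 1–2%.
- Lighter mass (early 10% against 35%, late 5% against 10%): early 1.60 against 1.67, pooled 1.29 against 1.32.
- Heavier mass (early 15% against 60%, late 10% against 20%): early 2.22 against 2.56 (13%), pooled 1.59 against 1.72 (8%).

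**The case against.** **The effect is trivial on the plan's own figures.** This stands: about 1% of the HR, well inside its standard error.

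**A single Day 21 spike is assumed.** This also stands in large part. Under Table 4 only missing-urine-only first weeks take a fixed date; other relapses take actual days, and the Week 4 visit window alone runs from Day 24 to Day 30. Induction may occur as late as week 22, so not every late induction is an early failure. The documents do not settle whether the first cluster sits on Day 21 or on an adjacent window start.

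**A spike followed by equal hazards is non-proportional, so there is no single true HR.** Correct for the step 5 and 6 scenarios: those figures are differences between two approximations, with the grouped-data fit as reference. In step 4 a true HR exists, and Efron recovers it. SAP 5.3.3 adds a time-dependent term if proportionality fails, but that model would be fitted in PHREG with the same tie handling.

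**The printed code is a skeleton.** It gives no censoring value for STATUS and leaves CTP and STRATA out of CLASS, so it must be edited anyway. The missing option is therefore weak evidence of a decision to use Breslow. It does leave the method unstated.

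**A stronger reading is tempting:** that Breslow makes the primary log HR some 17–18% too small. That follows from applying .85 against .60 initiation to all 300 per arm, with every non-inducted participant failing on Day 21 (HR 1.48 against 1.60). The documents do not support it. The .25 concerns early randomizers only, about 250 of 600; it is a detectable difference, not an expected rate; and the common date is assumed.

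**Conclusion.** The tie method is unspecified, and under PHREG's default it attenuates the primary HR whenever the arms differ. The direction is firm; the size is modest:
- about 1% under the planning exponential;
- about 2–3% pooled and about 5–7% in early randomizers if a .25 early induction gap all falls on one date, less if the dates spread;
- up to 8% pooled and 13% early only with the heavier mass assumed in step 6.

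All but the first rest on a Day 21 distribution that the documents do not give. The interaction decision can also move (67.5% against 74.8% of trials in the assumed scenario). Week 24 success rates do not depend on the tie method.

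A reader might further infer poor interval coverage or a marked loss of power for the primary analysis. Demonstrating that took inputs such as a true HR of 2.0 or 1.36 with 25% of BUP-NX events on Day 21, which have no source in the documents. This is a free improvement to the specification, not a defect that invalidates the analysis.

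**What to change.** In SAP 5.3.3, end the model statement with `/ TIES=EFRON` (or `TIES=EXACT`) and name the method in the text. Use the same option in the Cox models of SAP 5.4 and 5.6 and in the sensitivity analysis of SAP 6.0. `RISKLIMITS` has no bearing on ties and is not needed for this purpose.

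The cost is one option in code that already needs editing; data, recruitment and the stated power do not change. Make the change before analysis, because a tie method chosen after results are seen would look post hoc.
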